8. DATA COLLECTION AND MANAGEMENT

- Standardized photos and 3D scans at baseline and follow-up.
- Pseudonymized data stored on encrypted servers at Dental Esthetic BCN, GDPR compliant.
- Data preserved 15 years, then securely destroyed. • Investigator and promoter maintain separate encrypted linkage file.

9. STATISTICAL ANALYSIS PLAN (SAP)

Sample Size

30 participants (27 required for detecting a ≥ 2 -point VAS reduction; $\beta=0.80$, $\alpha=0.05$).

Analysis Methods

Descriptive Statistics

Mean \pm SD, median [IQR], and proportions.

Primary Analyses

- **FDI scores (ordinal):**

Friedman repeated-measures test + Holm correction

or ordinal mixed-effects model (time = fixed, participant = random)

- **VAS sensitivity (continuous):**

Linear mixed-effects model

or repeated-measures ANOVA (Greenhouse-Geisser correction)

Survival Analysis

- Kaplan–Meier survival curve
- Failure = debonding or fracture requiring replacement

Performance Threshold Tests

- FDI success proportion at 12 months with 95% CI
- One-sample binomial test vs threshold $\geq 80\%$
- Mean VAS reduction ≥ 2 points with CI >0

Missing Data

- Missing-at-random assumption
- Mixed models inherently robust; no imputation planned

Interim Analysis

None planned.

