3. STUDY DESIGN

A prospective, single-arm, monocentric, interventional clinical study with 12-month follow-up.

Number of participants: 30 adolescents (10–16 years old).

Study duration: 18 months.

Follow-up: Baseline, 48 h, 1 m, 3 m, 6 m, 12 m.

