6. OUTCOME MEASURES

Primary Outcomes

1. **FDI Global Acceptability (Success = all domains ≤ 3)** at 12 months
2. **Postoperative sensitivity (VAS 0–10)** at baseline, 48 h, 1, 3, 6, 12 months

Secondary Outcomes

- Patient satisfaction (Likert 1–5)
- Structural preservation (volumetric analysis of 3D scans)
- Vitality retention

- Restoration survival (Kaplan–Meier)
- Workflow efficiency (chair time, adjustments)

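### The sample-size statement prints β = 0.80, which means 20% power; 0.80 was almost certainly meant as the power itself

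*Protocol*

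**What the plan says.** Section 9 of the protocol, under Sample Size, plans 30 participants and justifies the number in one parenthesis: "27 required for detecting a ≥ 2 -point VAS reduction; $\beta=0.80$, $\alpha=0.05". It does not define β, use the word power, name a test, say whether α is one- or two-sided, or give an SD for the change. No other section states a power.

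Two other sections bear on the calculation. Section 6 lists sensitivity as a primary outcome and fixes its scale: "Postoperative sensitivity (VAS 0–10) at baseline, 48 h, 1, 3, 6, 12 months". Section 3 describes the design as "A prospective, single-arm, monocentric, interventional clinical study with 12-month follow-up", so a reduction can only be a within-participant change from baseline.

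**The concern.** In a sample-size statement that also gives α, β denotes the probability of a type II error, and power is 1 − β. Read that way, the protocol says the trial would fail to detect a 2-point reduction four times out of five. The likely explanation is that 0.80 is the power and the wrong symbol was printed.

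This is the only justification for the number of adolescents enrolled and the only figure from which a power can be read. An ethics committee, registry reader or journal reviewer who takes it at its word gets the wrong power. With no SD or sidedness printed, they cannot rework the calculation to confirm what was intended.

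**Working it through.** **Inputs from the protocol.** Required n = 27; difference δ = 2 points; α = 0.05; printed β = 0.80 (all Section 9). VAS range 0 to 10 (Section 6), so an individual change lies between −10 and +10. Single arm (Section 3).

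**Assumptions.** The calculation was a paired t-test on change from baseline. Sidedness and SD are not given, so both sidedness options are tried and the SD is solved for.

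**Step 1: the printed value.** Power = 1 − β = 1 − 0.80 = 0.20.

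**Step 2: reproducing 27.** It cannot be reproduced directly, because the SD is missing. Instead, find the SDs for which 27 is the smallest sufficient n. With standardised effect d = 2/SD, power comes from the noncentral t distribution with 26 degrees of freedom and noncentrality d√27. At n = 27 two-sided, power 0.20 is reached at d = 0.223 (SD = 2/0.223 ≈ 8.98) and power 0.80 at d = 0.560 (SD = 2/0.560 ≈ 3.57). These are the upper ends of the ranges; the lower ends are where 26 participants would already suffice.

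| Power | SD giving n = 27, two-sided | SD giving n = 27, one-sided |
|---|---|---|
| 0.20 (literal) | 8.81–8.98 | 12.36–12.60 |
| 0.80 | 3.50–3.57 | 3.99–4.06 |
| 0.90 | 3.03–3.08 | 3.39–3.45 |

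**Step 3: the ceiling on the SD.** For a change X bounded by ±10 with mean reduction 2, E[X²] ≤ 100, so SD ≤ √(100 − 2²) = √96 = 9.80. The one-sided literal reading (12.36 or more) is impossible. The two-sided one (8.81 or more) is not excluded by this bound.

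**Step 4: what the two-sided literal reading would require.** Take its lowest SD, 8.81, and count a reduction as positive.
- E[X²] = 8.81² + 2² = 77.6 + 4 = 81.6.
- Since |X| ≤ 10, X² ≤ 10|X|, so E|X| ≥ 81.6/10 = 8.16.
- The mean worsening part is (E|X| − E[X])/2 ≥ (8.16 − 2)/2 = 3.08.
- No one can worsen by more than 10 points, so the share worsening is at least 3.08/10 ≈ 31%. At SD 8.98 the same steps give 32%.

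The average participant would move by more than 8 of 10 points, and about a third or more would get worse while the mean improves by 2.

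**Step 5: the same check from the other side.** At illustrative two-sided SDs of 3, 3.5 and 4, 20% power needs 5, 6 and 7 participants; 80% power needs 20, 27 and 34.

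**The case against.** The strongest reply is that this is a slip of notation. Any statistician who sees 0.80 next to α = 0.05 reads it as power; nothing has been miscalculated, and the number of participants, the analysis and enrolment all stay the same. Most of that stands. The remedy is one line, and the point is no evidence that the trial is too small. But the protocol does state a parameter, and states it wrongly, in its only sample-size rationale. A separate analysis plan would not make that sentence correct.

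A second reply is that if 0.80 was almost certainly the power, a reader does recover it, so the 0.90 row is beside the point. It is fair that nothing in the text suggests 0.90, and that n alone never fixes power when the SD is unknown. The row shows only that 27 cannot serve as confirmation: the intended value is a strong inference from the printed 0.80, and the original calculation has to settle it.

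Third, asking for the test, sidedness and SD reaches past the β error into detail that a protocol may leave to an analysis plan. Their absence is not the finding here. They are requested because they are the means of verifying the corrected value.

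Fourth, the SD ranges depend on an assumed paired t-test, whereas Section 9 analyses the VAS with a mixed model or repeated-measures ANOVA. That is so, but the error itself follows from the definition of β. The ranges only support the inference about what was meant.

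Finally, the text was converted from PDF, and a leading 1 − could have been lost. The neighbouring symbols read cleanly and nothing points to such a loss; a glance at the source page settles it.

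**Conclusion.** The point holds. As printed, the protocol gives a type II error of 80%, hence 20% power, and no other statement corrects it. That β and the printed 27 are not plausibly compatible: the one-sided case is impossible on a 0–10 scale, and the two-sided case needs an SD close to its ceiling. Reading 0.80 as power gives an SD of about 3.5 to 4.1, well inside the scale.

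The misstatement is certain by definition. That 0.80 was meant as power is a well-supported inference which rests, for its numerical part, on the paired t-test assumption. The error concerns the stated power only; whether 27 or 30 participants suffice depends on an SD that the protocol does not give. It should be corrected, but it does not invalidate the design.

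**What to change.** In Section 9, Sample Size, replace the β value with power = 0.80 (β = 0.20), if that is the value the original calculation used. In the same sentence, state the test, the sidedness and the SD of change that produced 27. These must come from that calculation and not be chosen afterwards to fit. If the original inputs do not return 27 at that power, state the power that 27 or 30 participants actually deliver.

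The cost is one corrected line. Enrolment does not change.

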2. STUDY OBJECTIVES AND HYPOTHESIS

Primary Hypothesis

Graphene-reinforced CAD/CAM indirect restorations provide high clinical acceptability at 12 months, according to predefined FDI criteria, while reducing postoperative hypersensitivity relative to baseline and preserving structural tooth integrity.

Primary Objective

Evaluate the overall clinical performance of graphene-reinforced CAD/CAM inlays/onlays/overlays in MIH-affected molars at 12 months.

Secondary Objectives

- Assess FDI domain scores: marginal integrity, surface roughness, color stability, fractures, proximal contacts, occlusion/function, and soft-tissue response.
- Measure postoperative sensitivity using VAS.
- Assess patient-reported satisfaction.
- Evaluate structural preservation via pre/post 3D scans.
- Measure restoration survival (Kaplan–Meier).
- Assess workflow efficiency (chair time, need for adjustments).

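### The primary VAS analysis may be a mixed model or a repeated-measures ANOVA, but the missing-data rule fits only the mixed model

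*Protocol*

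**What the plan says.** Protocol section 6 makes VAS sensitivity one of two primary outcomes, recorded on the schedule in section 3: "Follow-up: Baseline, 48 h, 1 m, 3 m, 6 m, 12 m". The primary hypothesis in section 2 is framed at 12 months, "while reducing postoperative hypersensitivity relative to baseline".

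Protocol section 9, Primary Analyses, lists for VAS "Linear mixed-effects model" and then "or repeated-measures ANOVA (Greenhouse-Geisser correction". Neither is labelled primary or sensitivity, and no rule for choosing is given. Under Missing Data the section states "Missing-at-random assumption" and "Mixed models inherently robust; no imputation planned", and nothing else.

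The Sample Size lines plan 30 participants, with "27 required for detecting a ≥ 2 -point VAS reduction". The Performance Threshold Tests include "Mean VAS reduction ≥ 2 points with CI >0"; that line names neither a method nor a time point.

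**The concern.** The missing-data rule rests on a property that only one of the two permitted methods has. A likelihood-based mixed model uses every observed value and, if correctly specified, is valid under missing at random. Classical repeated-measures ANOVA with a Greenhouse-Geisser correction needs a full set of six values per participant. Without imputation, one missed visit removes the participant, and the result is in general valid only if data are missing completely at random.

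Two things are at stake. The primary method can be settled after both results are known, in a single-arm study where a fixed primary analysis is an important safeguard. If the 2-point reduction is taken from the ANOVA's analysis set, the analysed number can also fall below the stated 27 and the estimate can be biased under the plan's own assumption.

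**Working it through.** **Inputs from the protocol:** 30 enrolled, 27 required, a 2-point reduction, α = 0.05, power 0.80 (printed as β), five post-baseline visits. The protocol gives no SD of change, no sidedness and no missed-visit rate, so everything below that depends on them is an assumption.

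**The plan's own figure.** Without an SD, 27 can only be back-solved. For a paired t-test, two-sided 0.05, with noncentrality √n × 2/SD, 80% power at n = 27 needs a standardised effect of 0.560. The implied SD of change is 2/0.560 = 3.57. A smaller SD of 2.5 is carried alongside.

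**Complete cases under the ANOVA option.** For a miss rate q per visit and independent misses, the expected number is 30(1−q)^5. For misses clustered within participants (beta-binomial, correlation ρ), the chance of no miss in five visits is the product over i = 0 to 4 of (b+i)/(s+i), with s = (1−ρ)/ρ and b = (1−q)s.

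| q per visit | Independent | Chance of fewer than 27 (independent) | ρ = 0.2 | ρ = 0.5 |
|---|---|---|---|---|
| 2% | 27.1 | 32% | 27.9 | 28.7 |
| 3% | 25.8 | 63% | 27.0 | 28.0 |
| 5% | 23.2 | 93% | 25.1 | 26.7 |

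A simple paired change needs only baseline and 12 months: 30(1−q) = 29.4, 29.1 and 28.5 at these rates, and 27.0 at q = 10%.

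**Power of the paired comparison** at n = 27, 25.8 and 23.2:
- SD of change 3.57: 0.80, 0.78, 0.73.
- SD of change 2.5: 0.98, 0.97, 0.96.

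**Bias of the complete-case reduction.** Simulation with n = 30, six visits, mean VAS falling from 6 to 4 (true reduction 2.0) and constant correlation 0.5, so that the SD of change equals the visit SD. The log-odds of a miss shift by ±0.25 or ±0.5 per VAS point. This gives 3.4% to 8.1% missed per visit and 21.4 to 25.5 complete participants; 8,000 runs per cell, Monte Carlo SE at most 0.009.

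| Misses depend on | SD of change | Mean estimate, high-pain participants skip | Mean estimate, low-pain participants skip | Distance from 2.0 |
|---|---|---|---|---|
| Baseline VAS | 2.5 | 1.65 to 1.86 | 2.13 to 2.35 | 0.13 to 0.35 |
| Baseline VAS | 3.57 | 1.46 to 1.78 | 2.23 to 2.55 | 0.22 to 0.55 |
| Preceding visit | 2.5 | 1.92 to 1.97 | 2.02 to 2.08 | 0.02 to 0.08 |
| Preceding visit | 3.57 | 1.87 to 1.94 | 2.05 to 2.13 | 0.05 to 0.13 |

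If misses are unrelated to VAS there is no bias. For a simple paired change the bias is at most 0.10 (SD 2.5) or 0.18 (SD 3.57) under the baseline mechanism, and about 0.01 under the preceding-visit mechanism. An unstructured likelihood model on all observed data, run at SD 2.5, gave 1.97 to 2.02 throughout.

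**Does the mixed model's covariance matter?** With complete data, n = 30, SD 2.5 and correlation fading by a factor of 0.6, 0.75 or 0.85 per visit, a nominal 95% interval for 12 months minus baseline covers 89.8%, 87.3% and 84.9% with a random intercept alone. With an unstructured covariance it covers 95.2%, 95.1% and 95.1%. Under constant correlation 0.5 both cover about 94.6%.

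**The case against.** The strongest reply is that the plan already points to the mixed model: it is listed first, and the missing-data lines mention nothing else. On that reading the ANOVA is reserved for complete data, where it raises no missing-data problem. This reading is reasonable, but the text does not state it, and nothing prevents the ANOVA from being reported with incomplete data. A separate SAP might settle the choice, but section 9 is itself titled as the SAP and states both methods together with a rule that suits one.

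Second, the harm depends on a link the plan does not make. An omnibus ANOVA does not itself yield a mean reduction with an interval, so the 2-point line may mean a simple paired change, for which loss and bias are much smaller. This stands: a fall below 27 follows only on one reading. The time point can also be inferred as 12 months from section 2, though the threshold line does not say so.

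Third, the larger bias figures need strong inputs. A log-odds of 0.5 per point is an odds ratio of about 148 across a 0–10 scale (e^5). At SD 3.57 the normal model puts about 13% of baseline values above 10. When values are clipped to the scale, the true reduction in that cell shrinks to about 1.67 and the SD of change to about 3.1, although at about 5% missed per visit a bias of about 0.24 to 0.41 remains under the baseline mechanism. The 0.55 should carry little weight. The requirement in section 4 that participants be able to attend follow-ups lowers the risk further.

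None of this removes the inconsistency.

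**Conclusion.** The concern holds. A permitted primary analysis of a primary outcome does not fit the plan's stated missing-data assumption, and the choice of method is open. That conclusion rests on the text and on the standard behaviour of repeated-measures ANOVA, and it is firm.

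The numerical consequence is conditional. Power loss is modest at the implied SD and negligible at 2.5. Bias is appreciable if missed visits follow baseline pain, small if they follow the preceding visit's pain, and absent if they are unrelated to VAS. The case for changing the plan is consistency and a fixed primary method, not large expected error.

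Friedman versus the ordinal mixed model for FDI scores over time is the same mismatch in principle; no harm was quantified there. The 12-month FDI proportion and its binomial test are not affected.

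**What to change.** - Name the linear mixed model as the sole primary VAS analysis: visit as a categorical fixed effect, baseline in the response vector, unstructured within-participant covariance, Kenward-Roger degrees of freedom.
- Pre-state the fallback if it does not converge: heterogeneous Toeplitz, then a spatial-power structure in time plus a participant random intercept, because visits are unequally spaced. Do not rely on a random intercept alone.
- Take the 12-month minus baseline contrast and its 95% CI from this model, and say that the VAS threshold line uses it.
- Relabel the repeated-measures ANOVA as a complete-case sensitivity analysis, reported with its n.
- For FDI scores over time, use the ordinal mixed model where it converges and label any Friedman result complete-case with its n. Leave the 12-month binomial test as it is.

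The cost is a few edited lines and slightly more modelling, with no extra patients or data. An unstructured covariance over six visits has 6 × 7/2 = 21 parameters for 30 participants and may fail to converge, hence the fallback; the ordinal model may also fail at this size. The essential edits are naming the mixed model, tying the contrast to it and relabelling the ANOVA. The covariance and degrees-of-freedom choices are a workable way to carry them out.

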7. SAFETY AND ADVERSE EVENTS

Adverse events include:

- Persistent pain >72 h
- Severe hypersensitivity (VAS ≥ 7)
- Soft-tissue inflammation
- Partial or total restoration failure
- Complications requiring reintervention

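### The survival analysis counts only debonding or fracture as failure, although the outcome is labelled restoration survival without limit by cause; any loss for another reason would make the estimate too high

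*Protocol*

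**What the plan says.** The protocol names the outcome twice without restricting the cause of loss. Section 2 lists it as a secondary objective ("Measure restoration survival (Kaplan–Meier") and section 6 as a secondary outcome ("Restoration survival (Kaplan–Meier").

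Section 9, under Survival Analysis, fixes the event: "Failure = debonding or fracture requiring replacement". Two causes are named and there is no category for anything else.

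Other parts of the protocol foresee other ways in which a restoration can go wrong:

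- Section 7 lists as adverse events "Partial or total restoration failure", "Complications requiring reintervention" and "Severe hypersensitivity (VAS ≥ 7". The first two carry no limit by cause.
- Section 6 follows "Vitality retention" as a separate secondary outcome.
- Section 6 also sets the primary outcome "FDI Global Acceptability (Success = all domains ≤ 3", judged at 12 months.

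None of these enters the failure rule in section 9.

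**The concern.** A reader who sees a 12-month restoration survival figure will take it as the share of restorations still in place. Under the section 9 rule it is something narrower: the share that have not debonded or fractured. A restoration taken out because of a pulpal complication, intolerable sensitivity or marginal breakdown is gone, yet it is not an event. The label and the rule therefore describe different quantities, and the difference always favours the restoration.

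There is a second, smaller problem in the same line. The replacement condition may qualify fracture only, or both debonding and fracture. A restoration that debonds and is cemented back is an event on the first reading and not on the second. These restorations are adhesively cemented (section 5), so the case is foreseeable. If it is left open, the choice could be made after the data are known.

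What is at stake is the credibility of one secondary outcome. No test, threshold or sample size in section 9 rests on it.

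**Working it through.** **Inputs**

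- 30 participants, followed for 12 months (section 3).
- Number of restorations: not stated. Assumed here to be one per participant, so 30.
- Failure rule: debonding or fracture only (section 9).
- Rate of loss from other causes: not stated. Varied here from 0 to 4 of 30.
- Debonding/fracture failures: not stated. Varied from 0 to 3 of 30.
- No loss to follow-up, for simplicity.

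The protocol gives no expected survival rate, so there is no survival figure of its own to reproduce. Its one sample-size figure (27 required, 30 enrolled) concerns the VAS and does not bear on this point.

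**Direction**

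The Kaplan–Meier estimate is S = Π(1 − d/n) over the event times, where d is the number of events and n the number at risk. Each additional event puts another factor below 1 into the product. Counting other-cause losses can therefore only lower S or, if there are none, leave it unchanged. So the written rule gives a figure equal to or above any-cause restoration survival.

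**Size**

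Let m be the number of debonding/fracture failures and o the number of other-cause losses.

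- Any-cause survival: 1 − (m + o)/30.
- Written rule, other-cause losses left at risk: 1 − m/30.
- Difference: o/30, which is 3.3 points per loss (1/30 = 0.033).

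If the other-cause losses are censored instead, the written-rule figure changes very little. With m = 1 and o = 1, it is 1 − 1/29 = 96.6% if the other loss comes first and 1 − 1/30 = 96.7% if it comes second. Any-cause survival is 28/30 = 93.3% in both cases.

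The table takes m = 2. The censored column averages 2,000 simulations with event times uniform over the 12 months.

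| Other-cause losses (o) | Written rule, left at risk | Written rule, censored | Any cause |
|---|---|---|---|
| 0 | 93.3% | 93.3% | 93.3% |
| 1 | 93.3% | 93.2% | 90.0% |
| 2 | 93.3% | 93.1% | 86.7% |
| 3 | 93.3% | 93.0% | 83.3% |
| 4 | 93.3% | 92.8% | 80.0% |

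Over m = 0 to 3, the excess of the written rule (censored) over any-cause survival is 0 points with no other-cause loss, 3.2–3.3 with one, 6.3–6.7 with two, 9.4–10.0 with three and 12.6–13.3 with four. Censoring these losses or leaving them at risk changes the written-rule figure by less than 1 point, so the result does not depend on which is done.

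**Illustration (assumed counts)**

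Suppose there is no debonding or fracture and two restorations are replaced for other reasons.

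- Written rule: 30/30 = 100%. Exact 95% lower limit: 0.025^(1/30) = 88.4%.
- Any cause: 28/30 = 93.3%. Exact 95% lower limit: the p that solves P(X ≥ 28) = 0.025 with n = 30, which is 77.9%.

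**Ambiguity**

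On the same 30-restoration assumption, each debonded and re-cemented restoration moves the estimate by about 1/30 = 3.3 points according to the reading chosen. This holds even if nothing is lost for another cause.

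**The case against.** The strongest defence is that a cause-specific rule is legitimate and is stated in advance. The study evaluates a material, and detachment and fracture are coherent ways for a material to fail. On this view only the label is too broad. That is right as far as it goes: relabelling would remove the mismatch, and any-cause failure is not the only correct definition. As written, however, the protocol neither narrows the label nor treats other losses as competing events.

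The defence can add that the trial may see few such losses. Section 4 requires vital, restorable teeth and excludes extensive active caries, irreversible pulpitis and severe bruxism. Vitality, FDI acceptability and adverse events are also reported separately. This lowers the likely size of the problem and the risk that such losses go unreported. It does not correct the survival curve.

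Four stronger readings are tempting, and the documents do not support them:

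- **That survival will be overstated.** This needs at least one loss from another cause, and the protocol gives no rate.
- **That replaced restorations are informatively censored.** The protocol states no censoring rule, and such detail is commonly left to a separate analysis plan. The excess arises whichever way these losses are handled.
- **That survival would contradict the FDI success proportion.** Acceptability on every domain at 12 months and time to debonding or fracture are different quantities. They may differ under any definition of failure, and a domain score above 3 is not a stated reason for replacement.
- **That the adverse-event list contradicts section 9 outright.** Section 7 leaves restoration failure undefined. It is wider in wording, but that alone is not a contradiction.

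**Conclusion.** The point holds in a limited form. Section 9 fixes a two-cause failure rule for an outcome that sections 2 and 6 name without limit by cause. Followed as written, the rule yields a figure that can only equal or exceed the survival its label promises. The excess is about 3.3 points for each restoration lost or replaced for another reason, and zero if there is none. The 3.3 points assume 30 restorations, one per participant, and no loss to follow-up; the number of other-cause losses is unknown. Separately, the failure wording does not settle whether a re-cemented debonding is an event.

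This affects a secondary outcome and leaves the primary analyses unchanged. It should still be corrected before data are analysed, because it is a stated rule that can give a wrong result, not a detail left for later.

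**What to change.** In section 9, define failure for restoration survival as the first loss, removal or replacement of the restoration for any cause. Report debonding and fracture as a cause-specific component.

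If only the narrow rule is kept, label the outcome survival free of debonding or fracture in sections 2, 6 and 9, and treat loss for any other cause as a competing event.

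In either case, state in advance whether a debonded and re-cemented restoration is an event. The documents give no basis for preferring one answer; what matters is that it is fixed beforehand. Use the same meaning of restoration failure in sections 7 and 9.

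The cost is a sentence or two. Little or no new data should be needed, because restoration failures and reinterventions are already to be recorded as adverse events. The downside is that reported survival may be slightly lower.

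### The VAS threshold test uses the planning effect of 2 points as its cut-off but compares the interval only with 0, so the stated power does not describe it and meeting it does not show a 2-point reduction

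*Protocol*

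**What the plan says.** Three statements in Section 9 of the protocol bear on this point.

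- Sample Size: "27 required for detecting a ≥ 2 -point VAS reduction", with α 0.05 and a value of 0.80 printed as β. Thirty participants are planned. No SD of change, sidedness or larger expected reduction is given.
- Performance Threshold Tests, VAS: "Mean VAS reduction ≥ 2 points with CI >0". The line names no confidence level and no time point.
- Performance Threshold Tests, FDI: "One-sample binomial test vs threshold", the threshold being 80%.

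Section 6 makes VAS sensitivity a primary outcome: "Postoperative sensitivity (VAS 0–10) at baseline, 48 h, 1, 3, 6, 12 months". The primary hypothesis in Section 2 asks for "reducing postoperative hypersensitivity relative to baseline" and names no minimum size.

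**The concern.** Two points is both the effect on which the trial is sized and the hurdle for the observed mean. An estimate falls below its own true value about half the time, so a treatment that works exactly as planned has roughly an even chance of missing the benchmark. A reader who takes the sample-size statement to cover the threshold test would expect 80%.

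The second problem is what a pass means. The interval has to clear 0, not 2, so nothing in the criterion allows for uncertainty around 2. The FDI line in the same list does test against its own threshold. Under a heading that promises threshold tests, a met VAS criterion in a single-arm trial could be reported as at least 2 points shown, which the criterion cannot support.

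**Working it through.** **Inputs.** From Section 9: planning effect 2, α 0.05, 27 required, 30 planned. Assumed: 0.80 is power; the CI is a two-sided 95% t interval on within-patient change; SD of change is 2, 3 or 4 (5 as an extreme), because the protocol gives none.

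**1. The plan's own figure.** The figure of 27 cannot be reproduced without an SD, but the SD that yields it can be found. For a two-sided test against 0, normal approximation: SD = 2 × √27 / (1.960 + 0.842) = 10.392 / 2.802 = 3.71. The exact t version gives 3.57; one-sided, the values are 4.18 and 4.07. These are possible on a 0–10 scale, so 27 is compatible with a test against 0.

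**2. The criterion at a true reduction of 2.** For symmetric changes P(mean ≥ 2) = 0.50 whatever n and SD, and the CI clause can only lower it.

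| SD (n = 27, normal data) | 2 | 3 | 3.57 | 4 | 5 |
|---|---|---|---|---|---|
| Mean ≥ 2 and CI above 0 | 50% | 50% | 50% | 50% | 46% |
| CI above 0 alone | 99.9% | 92% | 80% | 71% | 52% |

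With n = 30 the first row stays at 50% for SD 2 to 4 and is 48% at SD 5. More participants do not lift it.

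**3. Non-normal changes with a true mean of 2.**

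- Right-skewed gamma, SD 2 and 3: 47% and 46%.
- Changes of 0 or 10 only, n = 27: 46%.
- Left-skewed gamma: about 52%.
- Whole-number changes from 0 to 4: 53%.
- Changes of 3 or 0 (probabilities 2/3 and 1/3): 59% at n = 27, 58% at n = 30.
- Changes of +3 (80%) or −2 (20%): the mean reaches 2 when 3k − 2(n − k) ≥ 2n, that is k ≥ 4n/5. For n = 27, P(k ≥ 22) = 0.54; for n = 30, P(k ≥ 24) = 0.61.

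The examples therefore run from about 46% to 61%.

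**4. How often the CI clause matters.** The lower limit exceeds 0 when s < mean × √n / t. At an observed mean of 2 and n = 27: s < 2 × 5.196 / 2.0555 = 5.06. At n = 30: s < 2 × 5.477 / 2.0452 = 5.36. Below these SDs the criterion is simply an observed mean of at least 2.

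**5. What a pass shows.** At an observed mean of 2.0 and n = 27, the 95% CI is 2 ± 2.0555 × SD / √27: 1.2–2.8 (SD 2), 0.8–3.2 (SD 3), 0.4–3.6 (SD 4). All three pass. At a true reduction of 1.5, P(mean ≥ 2) = 1 − Φ(0.5√27 / SD): 10% / 19% / 26% for SD 2 / 3 / 4.

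**6. What would show at least 2 points.** A lower 95% limit of at least 2 is reached 2.5% of the time at a true 2 (normal data, any SD). An 80% chance of it needs a true reduction of about 3.1 / 3.7 / 4.2 for SD 2 / 3 / 4 (n = 27).

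**7. Illustration at the back-solved SD of 3.57, n = 27.** CI above 0 is met 80% of the time at a true 2, the joint criterion 50%. For 80% on the joint criterion the true reduction must be about 2 + 0.842 × 3.57 / √27 = 2.58.

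**The case against.** The best defence is that the protocol states nothing false about power. To detect an effect ordinarily means to reject no change when that effect is true, step 1 shows that 27 fits this reading, and no sentence attaches the power to the threshold line. Requiring significance plus an observed relevance benchmark is also a legitimate dual criterion, and a pass rate near one half at the benchmark is a property of such rules. Section 2 asks only for some reduction, and no declaration of trial success or failure hangs on the VAS line.

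Much of this stands. It makes the power issue a mismatch between two lines of Section 9 rather than a wrong figure, and it limits the severity. It does not remove the second problem: a line listed as a threshold test at 2 points does not test 2 points.

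Three stronger readings are tempting and should be resisted.

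- A reader might infer that 50% is a hard ceiling for any n, SD and distribution. It is not: left-skewed or discrete changes exceed it, up to 61% in step 3.
- A reader might infer that the CI clause does nothing. If nobody worsened, the SD at a mean of 2 could not exceed √(2 × 8 × 27/26) = 4.08 and the clause could not bind at n = 27. But the protocol does not state that nobody worsens, and Section 7 lists severe hypersensitivity and persistent pain as adverse events. The clause rarely binds; it is not void.
- A reader might infer that the sample size is wrong or the trial underpowered. Without an SD the protocol supports neither conclusion.

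**Conclusion.** Wrong as written, minor to should-fix. The criterion is met about 50% of the time at the planning effect, so 80% power can belong only to the test against 0. A pass supports a reduction greater than 0 with an observed mean of at least 2, and no more.

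The figure of about 50% needs roughly symmetric changes but no SD. The pass rates at a true 1.5 and the interval widths rest on the assumed SDs and a 95% interval. The power comparison rests on reading the printed β as power; if it was meant literally, only that comparison falls, while the pass rate and the limit on the claim remain. The criterion is still strict evidence of some reduction. The Section 2 hypothesis and the mixed-model or repeated-measures ANOVA test are not affected.

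**What to change.** Keep the 2-point benchmark and add to Section 9:

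*The sample size and its power refer to the test of mean VAS change from baseline to [time point named by the sponsor] against 0, by [the named primary VAS analysis], assuming a true reduction of 2 points and an SD of change of [sponsor's value]. The criterion of an observed mean reduction of at least 2 points with CI above 0 is a relevance benchmark, met with a probability of about 50% at a true 2-point reduction. A reduction of at least 2 points will be claimed only if the lower 95% confidence limit is at least 2.*

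The time point and the analysis must be filled in, since Section 6 lists five post-baseline assessments and Section 9 offers two VAS models; otherwise the power still has no identifiable test. The power figure should be printed only once the sponsor has confirmed it with the stated SD.

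The cost is three sentences and those entries, with no added participants, visits or analyses. The drawback is a less favourable stated probability and a narrower claim: given the true reductions needed in step 6, a statement of at least 2 points may often not be available.
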